Echo, EST, Holter 4-7 days, AFSS, Serum and urine analysis. Conventional cardiovascular risk factor (CVRF) management as per treating physician	Holter 4-7 days, AFSS, Conventional CVRF management as per treating physician	Echo, EST, Holter 4-7 days, AFSS, Retinal examination, Serum and urine analysis. CVRF management as per treating Physician	Echo, EST, Holter 4-7 days, AFSS, Retinal examination, Serum and urine analysis. CVRF management as per treating Physician				

Additional electro-anatomical mapping to estimate scar burden along with CMRI will be offered to patients listed for AF ablation. The CMR will be repeated after 12 months to assess AAD in a year as per IMPULSE AF protocol (CALHN Ethics and Research Committee Approval R2010712)

Following assessments are standard for AF care and will be offered to all (control and intervention) participants.

a) Baseline Assessment

At baseline, following assessment will be performed for all participants:

- Weight and height recorded to calculate BMI.
- Demographics and conventional cardiovascular risk factors profiling by recording fasting glucose, lipid profile, age, gender, smoking history, systolic, diastolic, and pulse pressure.
- Brachial and aortic blood pressure (BP) assessment in a supine position after a resting period of 10 min by a mercury sphygmomanometer. Sphygmocor device will be applied to the right forearm over brachial artery to determine the central blood pressure indices as described previously (IMPULSE-AF protocol). Brachial blood pressure will be assessed by recording phase I and V of Korotkoff sounds to determine the brachial systolic and diastolic BP, respectively.
- Conventional 12-lead resting electrocardiograms (ECG) will be recorded and interpreted according to the Minnesota code (Mc).

Protocol for HIGH IMPACT- AF study

Centre For Heart Rhythm Disorders, Royal Adelaide Hospital, University of Adelaide

- Exercise stress test as per Bruce Protocol to assess exercise capacity.
- Blood will be drawn following a 12-hour fast to determine plasma lipids, fasting glucose, hs CRP and renal function.
- Trans-thoracic Echo (TTE) will be performed to assess Biventricular systolic and diastolic function along with left atrial size.
- 4 to 7days Holter monitoring to evaluate AF recurrence and arrhythmia burden

b) Exercise Tolerance Assessment

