Retinal photographs will be acquired from AF patients at baseline and during their follow up appointments yearly. Retinal vascular calibre will be measured from photographs using a validated computer program[22]. Retinal arteriolar and retinal venular calibre equivalents will be measured, and correlated with changes in central or peripheral blood pressures[22]. The acquisition of retinal image takes couple of minutes and it is a painless procedure that does not require any specific preparation.

[figure not shown]

Fig. 1. Sphygmocor applanation tonometry device (http://atcormedical.com/sphygmocor.html)

F. OUTCOMES OF THE STUDY

Primary outcomes to be evaluated include:

Association and Impact of central blood pressure control on AF outcomes (recurrence and AF burden).

Secondary Outcomes:

- Prevalence of central high blood pressure and aortic stiffness in AF patients with normal brachial BP.
- Association of brachial and central blood pressure indices including aortic stiffness to end organ insult and electro-anatomical remodeling of atria in AF patients.
- Correlating central blood pressure treatment target goals to proportionate decrease in events [Nephropathy (20% increase in ACR or 15-20% drop in estimated glomerular filtration rate (eGFR)), Left ventricular hypertrophy (LVH)/mass, LV diastolic dysfunction. Left atrial area and conduit vascular remodeling.
- Defining exaggerated BP response to exercise and postural change in our AF cohort and relating it with outcomes.
- > Number of anti-HTN required to achieve BP targets.
- Adverse events secondary to anti-HTN drugs including symptomatic postural BP drop of >20mmHg, acute kidney injury and electrolytes imbalance requiring hospitalization.

G. ETHICAL CONSIDERATIONS

Clinical Equipoise

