The study is a low risk, single blinded randomised trial to evaluate the impact and treatment of central high blood pressure on AF and CV outcomes. Central high blood pressure will be estimated by validated cuff based device (Sphygmocor) non-invasively. Vascular remodelling secondary to HTN, leads to aortic stiffness, which is a modifiable risk factor. At present, it is known that various anti-hypertensive agents can have significantly different effects on central aortic pressures despite similar brachial blood pressure valuation [23]. Agents such as inhibitors of the renin-angiotensin system and amlodipine could be started in individuals with increased aortic stiffness. As such, the investigators regarding the conduct of this study identify no specific ethical concerns.

Informed Consent

All patient participants will undergo a formal process of informed consent prior to study participation. Patients will be blinded with regard to their randomised group and will be treated for peripheral or central high blood pressure accordingly.

Drugs

No additional pharmaceuticals will be administered for the study protocol, with the exception of anti-HTN to achieve treatment target goals re central or brachial blood pressure. Side effects of anti HTN medication will be recorded by conventional clinical approach of reviewing the symptoms, documentation of postural drop in BP and monitoring of renal function tests during follow up or as required clinically.

Specific Safety Consideration

No significant increase in radiation dose is anticipated for the acquisition of electrophysiological data for the study because we are going to use 3D mapping to position the catheters in atria. The non-invasive assessment of blood pressure is not associated with any known risk. Retinal photography does not require any mydriatics.

H. ANALYSIS AND REPORTING OF RESULTS

Sample size calculation

Assuming the recurrence risk is 40% for AF in control, we estimate 90 patients in each group would give us 80% power to detect the 20% difference between groups at 5% significance level. Anticipating dropout rate of 28% over the course of the study, we would like to recruit 126 patients in each group.

Statistical Analysis

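### The drug-harm outcome counts electrolyte imbalance, and on the natural reading acute kidney injury, only when the patient is hospitalised, although the protocol records side effects without that condition

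*Protocol*

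**What the plan says.** Section F of the protocol (Secondary Outcomes) has one outcome for harm from treatment: "Adverse events secondary to anti-HTN drugs including symptomatic postural BP drop of >20mmHg, acute kidney injury and electrolytes imbalance requiring hospitalization". The words at issue are the last ones, "acute kidney injury and electrolytes imbalance requiring hospitalization". The section gives no laboratory definition of acute kidney injury or of electrolyte imbalance.

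Another secondary outcome in Section F counts a renal event from laboratory values, with no mention of admission: "Nephropathy (20% increase in ACR or 15-20% drop in estimated glomerular filtration rate (eGFR". It is listed among the events that treatment to target is expected to reduce.

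Section G (Drugs) describes how drug harm is collected: "Side effects of anti HTN medication will be recorded by conventional clinical approach of reviewing the symptoms", together with "documentation of postural drop in BP and monitoring of renal function tests during follow up or as required clinically". No admission threshold appears there. Section G (Clinical Equipoise) indicates the drugs in view: "Agents such as inhibitors of the renin-angiotensin system and amlodipine could be started in individuals with increased aortic stiffness".

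The test schedules are in Section D. Table 2 (intervention) names renal function tests at all six follow-up visits: 3, 6, 9, 12, 15 and 18-20 months. Table 3 (control) defines the abbreviation RFTs but uses it in no visit cell. Its 11-13 and 18-20 month visits list "Echo, EST, Holter 4-7 days, AFSS, Retinal examination, Serum and urine analysis". Section E(c), which describes the serum and urine analysis, names natriuretic peptide, endothelial, inflammatory and fibrosis markers and the urinary albumin-creatinine ratio. It names neither creatinine nor electrolytes. Renal function for all participants is named only at baseline (Section D, Baseline Assessment).

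**The concern.** The trial compares titration to central pressure targets with usual brachial targets, and the Introduction calls the former aggressive control. Its conclusion will rest on setting any AF benefit against drug harm. If a named harm counts only when it leads to admission, a laboratory disturbance found at a visit and managed without admission is not an event under that wording, even though Section G says it will be recorded.

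Two things follow. Admissions may be too few for the arms to be told apart, so similar counts would say little about safety. Admission is also a clinician's decision. Section G states blinding for patients only, and treatment is titrated to a target that differs by arm, so whoever decides on admission may know the allocation.

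**Working it through.** **1. The wording.** The closing qualifier in the Section F outcome can attach in three ways.

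- To electrolyte imbalance alone. That harm is then limited to admissions, and acute kidney injury counts without a definition.
- To acute kidney injury and electrolyte imbalance together. This is the natural reading, and both are limited to admissions.
- To every item in the list, including the postural drop.

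On each reading at least one named laboratory harm is counted only on admission.

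**2. The sections side by side.**

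| Place | What it does | Admission needed? |
|---|---|---|
| Section F, adverse events | Counts drug harm | Yes, for electrolytes at least |
| Section F, nephropathy | Counts an eGFR fall or ACR rise as end-organ disease | No |
| Section G, Drugs | Records side effects, using renal function tests | No |

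The collection rule is wider than the counting rule. Nephropathy covers part of the gap, but it does not attribute the event to a drug and it does not cover electrolytes.

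**3. Share left out.** The protocol gives no hospitalised share, so h is an assumption. If the qualifier applies, the share missed is 1 - h. For illustration, suppose a true event rate of 10% in 125 patients, which is 12.5 events per arm.

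| Assumed h | Counted (12.5 × h) | Share missed |
|---|---|---|
| 10% | 1.25 | 90% |
| 25% | 3.1 | 75% |
| 50% | 6.25 | 50% |
| 75% | 9.4 | 25% |

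**4. What rare events can show.** Power of the two-sided 5% Fisher exact test is the sum, over all pairs of counts with p ≤ 0.05, of the product of the two binomial probabilities. All rates are assumptions. The arm sizes come from the protocol: 125 per arm (Section C) and 90 per arm from the sample size calculation (Section H).

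| Assumed rates | Ratio | n = 125 | n = 90 |
|---|---|---|---|
| 1% vs 2% | 2 | 1.3% | 0.4% |
| 5% vs 10% | 2 | 23% | 17% |
| 10% vs 20% | 2 | 54% | 40% |
| 1% vs 3% | 3 | 6.3% | 2.4% |
| 5% vs 15% | 3 | 70% | 55% |

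Like should be compared with like. At a fixed ratio, power rises with the base rate, but a doubling from 5% is still poorly detected. Zero events in 125 leaves a one-sided 95% upper limit of 1 - 0.05^(1/125) = 2.4%. Five admissions against none at 125 per arm gives p = 0.06.

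**5. Can the arms be compared on laboratory values?** By name, renal function tests are scheduled at six follow-up visits in the intervention arm and at none in control. Counting from every available test would give the intervention arm more chances to show an event. Blood is scheduled in both arms at about 12 months (12 in Table 2, 11-13 in Table 3) and at 18-20 months. Whether the control sample includes creatinine or electrolytes is not stated, though the nephropathy outcome already needs creatinine for its eGFR limb.

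**The case against.** The strongest reply is that Section F introduces its harms with the word including, so the list is open. An outpatient creatinine rise attributed to a drug would still be an adverse event of treatment, and Section G says such effects will be recorded. The layout of safety tables is commonly left to the SAP, which is not at hand. The nephropathy outcome also counts a 15-20% eGFR fall without admission. Finally, hospitalised events do not depend on how often blood is scheduled, which is a real advantage when one arm is tested far more often.

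Much of this stands. A reader might infer that most renal and electrolyte harm would go unreported. The documents do not support that: recording is planned, the list is open, the reach of the qualifier is ambiguous, and no figure gives the hospitalised share. Missing more than half requires that share to be below 50%. A reader might also assume that the necessary laboratory values already exist in both arms. That is not established for control, and electrolytes are nowhere named as a scheduled measurement.

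The reply does not remove the counting rule. An open list admits other kinds of event; it does not lift a condition attached to one that is named. Recording an event is not the same as counting it in an outcome compared by arm. An eGFR fall counted as nephropathy would be read as end-organ disease.

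**Conclusion.** The point holds as a conflict between how drug harm is recorded and how it is counted. Non-hospitalised electrolyte disturbance, and on the natural reading non-hospitalised acute kidney injury, may be recorded under Section G yet fall outside the Section F harm outcome. The size of the loss is unknown: 25% to 90% of events over the assumed range of hospitalised shares. If admissions are as rare as 1% to 3%, power is at most about 6% at 125 per arm, so similar counts would not be evidence of equal safety. Laboratory-based counting improves on this only as far as events are more frequent. All of these rates are assumptions.

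The matter should be corrected because it bears on the benefit-harm comparison. It does not affect the primary outcome or the sample size.

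**What to change.** Reconcile Section F with Section G (Drugs):

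- Count acute kidney injury and electrolyte imbalance whether or not the patient is admitted, using one laboratory definition that the investigators state in advance and apply identically in both arms.
- Report hospitalised events as a separate serious line. This keeps the measure that does not depend on scheduled sampling.
- Base the between-arm comparison of laboratory-defined events on the proportion of patients affected at visits where both arms have renal function tested: about 12 months and 18-20 months.
- Confirm whether the control serum analysis in Table 3 includes creatinine and electrolytes, and limit the change to what is measured in both arms.

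The cost is a sentence in Section F, one safety table, and confirmation of the control panel, with an added assay if the investigators find one missing. There are two downsides. More events will be reported, most of them probably mild. A few scheduled samples will also miss transient events, so the laboratory comparison will not be a full count of harm.
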